**Table 6-5. Composite Estimand 2 (Sensitivity Analysis) for Clinical Remission by CDAI**

Attributes	Composite Estimand 2
Treatment	Filgotinib 200 mg, filgotinib 100 mg, or placebo
Population	Full Analysis Set as defined in Section 3.1.2
Subject-level endpoint	CDAI clinical remission status (Yes/No) at Week 10 for Induction Studies and at Week 58 for Maintenance Study If CDAI < 150, then the subject will be defined as achieving clinical remission at Week 10 or at Week 58, respectively. If the above remission criterion is not met, the subject will be considered as not achieving clinical remission by CDAI. If the CDAI is missing, then data will be analyzed using MICE as outlined in section 6.2.5.
Handling of missing data due to intercurrent events (subject-level endpoint)	Subjects who meet treatment failure criteria (ie, take potentially effective medications other than study treatment as defined in Appendix 6) or prematurely discontinue from the study without available assessment result are considered as not achieving clinical remission by CDAI
Population-level summary	Difference in proportions in clinical remission by CDAI, comparing a filgotinib dose group to placebo group

CDAI = Crohn’s Disease Activity Index

### 6.2.3.3. Endoscopic Response

Intercurrent events can impact subjects at the segment level (eg, stricture) or at the subject level (eg, early termination of the study) for SES-CD data. Similar to the estimand for clinical remission by CDAI, the definition of the estimand for endoscopic response is expanded to include 2 additional attributes. These 2 additional attributes are: (1) the segment level outcome to be measured; and (2) the handling of intercurrent events impacting the segment.

Using this expanded definition of an estimand and based on the definitions of the different types of estimands in the ICH E9(R1) guidance, the primary estimate of endoscopic response endpoint

will use a composite estimand (Table 6-6). A second composite estimand is also proposed as a sensitivity analysis (Table 6-7). For each estimand, the handling of missing data due to the intercurrent events will be expanded to the segment level in addition to the subject level.

**Table 6-6. Composite Estimand 1 (Primary Analysis) for Endoscopic Response**

Attributes	Composite Estimand 1
Treatment	Filgotinib 200 mg, filgotinib 100 mg, or placebo
Population	Full Analysis Set as defined in Section 3.1.2
Segment-level outcome to be measured	SES-CD subscore for each segment at baseline and Week 10 for Induction Studies and at Week 58 for Maintenance Study
Subject-level outcome to be measured	Endoscopic response status (Yes/No) at Week 10 for Induction Studies and at Week 58 for Maintenance Study  If the percentage reduction of total SES-CD from Induction baseline is $\geq 50\%$ , then the subject will be defined as achieving endoscopic response at Week 10 or at Week 58, respectively. If the above responder criterion is not met or total SES-CD is missing, the subject will be considered as not achieving endoscopic response.
Measure of intervention effect & handling of missing data due to intercurrent events (segment-level outcome)	If the subscore of a segment is missing at baseline, this segment will not be included in the calculation of the total SES-CD for all the visits. If the subscore of a segment is observed at baseline, but missing at Week 10 or Week 58, it will be imputed using a score of 12 (worst subscore from the sum of the 4 variables in a segment).
Measure of intervention effect & handling of missing data due to intercurrent events (subject-level outcome)	Subject who met treatment failure criteria (ie, take potentially effective medications rather than study treatment as defined in Appendix 6) or prematurely discontinued from study without available assessment result is considered a non-responder.
Population-level summary measure	Difference in proportions in endoscopic response, comparing a filgotinib dose group to placebo group

SES-CD = Simple Endoscopic Score for Crohn's Disease

**Table 6-7. Composite Estimand 2 (Sensitivity Analysis) for Endoscopic Response**

Attributes	Composite Estimand 2
Treatment	Filgotinib 200 mg, filgotinib 100 mg, or placebo
Population	Full Analysis Set as defined in Section 3.1.2
Segment-level outcome to be measured	SES-CD subscore for each segment at baseline and Week 10 for Induction Studies and at Week 58 for Maintenance Study
Subject-level outcome to be measured	Endoscopic response status (Yes/No) at Week 10 for Induction Studies and at Week 58 for Maintenance Study  If the percentage reduction of total SES-CD from Induction baseline is $\geq 50\%$ , then the subject will be defined as achieving endoscopic response at

	Week 10 or at Week 58, respectively. If the above responder criterion is not met, the subject will be considered as not achieving endoscopic response. If total SES-CD is missing, then data will be analyzed using MICE as outlined in section 6.2.5.
Measure of intervention effect & handling of missing data due to intercurrent events (segment-level outcome)	All segments will be included in the total SES-CD calculation regardless of being missing or not.
Measure of intervention effect & handling of missing data due to intercurrent events (subject-level outcome)	Subject who met treatment failure criteria (ie, take potentially effective medications rather than study treatment as defined in Appendix 6 ) or prematurely discontinued from study without available assessment result is considered a non-responder.
Population-level summary measure	Difference in proportions in endoscopic response, comparing a filgotinib dose group to placebo group

SES-CD = Simple Endoscopic Score for Crohn's Disease

#### 6.2.4. Primary Analysis of the Primary Efficacy Endpoints

Primary analysis will be conducted according to the composite estimand 1 specified in Section [6.2.3](#).

For the individual Induction Studies (Cohort A and Cohort B), a stratified Cochran-Mantel-Haenszel (CMH) test will be used to compare the treatment effect between a filgotinib dose group (eg, 200 mg) and placebo. The CMH tests will be stratified by the following factors:

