#### **8.5. Efficacy Analysis**

##### **8.5.1. Primary Analyses**

For each Induction Study (Cohort A and Cohort B), the primary analysis will compare a filgotinib dose group to placebo on the proportion of subjects achieving clinical remission by CDAI at Week 10 and the proportion of subjects achieving endoscopic response at Week 10. In the EU, for each Induction Study (Cohort A and Cohort B), the primary analysis will compare a filgotinib dose group to placebo on the proportion of subjects achieving clinical remission by PRO2 at Week 10 and the proportion of subjects achieving endoscopic response at Week 10. Similarly, for the Maintenance Study, the primary analysis will compare a filgotinib dose group to placebo on the proportion of subjects achieving clinical remission by CDAI at Week 58 and the proportion of subjects achieving endoscopic response at Week 58. In the EU, for the Maintenance Study, the primary analysis will compare a filgotinib dose group to placebo on the proportion of subjects achieving clinical remission by PRO2 at Week 58 and the proportion of subjects achieving endoscopic response at Week 58. For a dose group to demonstrate significant treatment effect over placebo, statistical significance needs to be achieved on both clinical remission by CDAI and endoscopic response end points at significance level that is specified in Section 8.5.3. In the EU, for a dose group to demonstrate significant treatment effect over placebo, statistical significance needs to be achieved on both clinical remission by PRO2 and endoscopic response end points at significance level that is specified in Section 8.5.3.

The Cochran-Mantel-Haenszel (CMH) approach adjusting for stratification factors will be used for hypothesis testing of each primary end point within each study. For calculation of reduction from baseline in SES-CD score in the endoscopic response, SES-CD score at screening will be used as baseline value. For calculation of CDAI and PRO2 scores, refer to [Appendix 4](#).

Subjects who do not have sufficient measurements to determine efficacy end points will be considered failures (ie, non-responder imputation [NRI]). Sensitivity analyses will be described in the SAP.

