### 3.3. Strata and Covariates

Subjects will be randomly assigned to treatment groups via IWRS using a stratified randomization schedule into each individual study (Cohort A Induction, Cohort B Induction, and Maintenance). Details of the randomization ratio and stratification variables for each study are provided in Section 1.2.

If there are discrepancies in stratification factor values between the IWRS and the clinical database (eCRF data), the baseline values recorded in the clinical database will be used for analyses. For the derivation of concomitant medication use at Day 1, the start date of such medication should be before or on the same date of the first dose of study drug and with either the stop date of such medication being on or after the first dose of study drug or with “ongoing” status.

Stratification factors will be used as covariates in evaluating efficacy endpoints, as specified in Section 6.

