**Table 6-1. Definitions of Selected Efficacy Endpoints**

Study	Type	Endpoint	Definition
Induction	EU: secondary Non-EU: Co-primary	Clinical remission by CDAI at Week 10	CDAI score < 150 points at Week 10
Induction	Co-primary	Endoscopic response at Week 10	≥ 50% reduction from baseline in total SES-CD score at Week 10 based on central reading
Induction	EU: co-primary Other: Secondary	Clinical remission by PRO2 at Week 10	Abdominal pain score ≤ 1 (on a scale of 0 to 3) and liquid or very soft stool (Bristol stool scale type 6 or 7) frequency ≤ 3 at Week 10
Induction	Secondary	Clinical response by CDAI at Week 10	Reduction in CDAI score from Induction baseline by at least 100 points or CDAI score < 150 at Week 10
Induction	CCI	CCI	CCI
Induction	EU: Secondary Non-EU: CCI	Both clinical remission by PRO2 and endoscopic response at Week 10	Clinical remission by PRO2 and endoscopic response at Week 10 combined into a single endpoint on a patient level
Induction	CCI	CCI	CCI
Induction	CCI	CCI	CCI
Induction	CCI	CCI	CCI
Maintenance	Co-primary	Clinical remission by CDAI at Week 58	CDAI score < 150 points at Week 58

Study	Type	Endpoint	Definition
Maintenance	Co-primary	Endoscopic response at Week 58	≥ 50% reduction from Induction baseline in total SES-CD score at Week 58 based on central reading
Maintenance	Secondary	Clinical remission by PRO2 at Week 58	Abdominal pain score ≤ 1 (on a scale of 0 to 3) and liquid or very soft stool (Bristol stool scale type 6 or 7) frequency ≤ 3 at Week 58
Maintenance	Secondary	Clinical response by CDAI at Week 58	Reduction in CDAI score from Induction baseline by at least 100 points or CDAI score < 150 at Week 58
Maintenance	Non-EU: secondary	Sustained clinical remission by CDAI at Weeks 10 and 58	Clinical remission by CDAI at both Week 10 and Week 58
Maintenance	Non-EU: secondary	6-month Corticosteroid-free clinical remission by CDAI at Week 58	Clinical remission by CDAI with no corticosteroid use for the indication of CD for at least 6 months prior to Week 58 among subjects who are on corticosteroid at maintenance baseline (baseline of Maintenance Study). Subjects who weaned off steroids but required re-initiation within 6 months prior to Week 58 assessment will be considered to have not met this endpoint.
Maintenance	Secondary	Sustained clinical remission by PRO2 at Weeks 10 and 58	Clinical remission by PRO2 at both Week 10 and Week 58

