##### Cohort A Induction Study:

- Number of prior exposures to biologic agent (0, 1, > 1) as listed in [Appendix 2](#)
- Concomitant use of oral, systemically absorbed corticosteroids at Day 1
- Concomitant use of immunomodulators at Day 1

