### Maintenance Study Stratification Factors:

- History of exposure to a biologic agent (yes, no)
- Concomitant use of oral, systemically absorbed corticosteroids at maintenance baseline (yes, no)
- Concomitant use of immunomodulators at maintenance baseline (yes, no)

Other subgroups for each individual study include:

- Age group on the date of first dose of the study drug (< 65 years, ≥ 65 years)
- Sex at birth (female, male)
- Race (Asian, Black or African American, White, and Other)
- Geographic region (US, non-US)
- CCI [REDACTED]
- CCI [REDACTED]
- Duration of CD (years from date of diagnosed to first dosing date of Induction study drug) (< 1 year, ≥ 1 to < 3 years, ≥ 3 to < 7 years, ≥ 7 years)
- Baseline disease activity (based on Induction baseline CDAI score) (< 300, ≥ 300)
- Induction baseline SES-CD score (< 16, ≥ 16)
- Previous exposure to TNF- $\alpha$  antagonist (yes, no)
- Prior TNF- $\alpha$  antagonist failure (yes, no)
- Previous exposure to vedolizumab (yes, no)
- Prior vedolizumab failure (yes, no)
- Dual refractory (yes, no)
- The following 4 subgroups:
  - US/Korean males who are dual refractory
  - US/Korean males who are not dual refractory
  - Non-US/Korean males (US/Korea females and subjects from countries other than US and Korea) who are dual refractory
  - Non-US/Korean males who are not dual refractory

For a subject, if the value of the grouping variable cannot be determined, this subject will be excluded from the corresponding subgroup analysis. Non-stratified risk difference between treatment groups will be evaluated for each of the subgroups using Fisher's exact test. A forest plot will graphically present the non-stratified risk difference and 95% CI using normal approximation with a continuity correction on the treatment differences (filgotinib – placebo) in each co-primary endpoint for each of the subgroups.

Additional subgroup analyses for geographic region may be added based on the distribution of study enrollment prior to study unblinding.

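### The Induction tests of CDAI and PRO2 remission leave out the baseline score already collected on every subject, which gives up a small to modest amount of precision

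*SAP*

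**What the plan says.** Protocol 8.5.1 sets the method: "The Cochran-Mantel-Haenszel (CMH) approach adjusting for stratification factors will be used for hypothesis testing of each primary end point within each study". SAP 6.2.4 repeats it for the Induction Studies, where "a stratified Cochran-Mantel-Haenszel (CMH) test will be used to compare the treatment effect between a filgotinib dose group (eg, 200 mg) and placebo", and lists three factors. They are the number of prior biologics (0, 1 or more than 1 in Cohort A; up to 1 or more than 1 in Cohort B), "Concomitant use of oral, systemically absorbed corticosteroids at Day 1" and "Concomitant use of immunomodulators at Day 1". The risk difference and its interval in the same section use the same strata. SAP 3.3 names no other covariate: "Stratification factors will be used as covariates in evaluating efficacy endpoints, as specified in Section 6". SAP 6.3.2 applies the same method to the key secondary endpoints.

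The non-EU clinical co-primary is a fixed cut-off, "CDAI score < 150 points at Week 10". PRO2 remission, the EU clinical co-primary, is also fixed: pain at most 1 and stool frequency at most 3 (SAP Table 6-1). Entry requires a CDAI from 220 to 450 (Protocol 4.2.1). Endoscopic response is different, being a reduction of at least 50% from the subject's own baseline SES-CD.

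Baseline CDAI is used elsewhere: as a subgroup factor in SAP 6.2.7, "Baseline disease activity (based on Induction baseline CDAI score", split at 300, and as a predictor in the imputation model of SAP 6.2.5.2. The visible text does not say why it is left out of the test.

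**The concern.** With a fixed target, the starting score sets the distance to cover. A subject entering at a CDAI of 220 must fall by just over 70 points to be below 150; one entering at 450 must fall by just over 300. If the baseline score predicts remission within arm, a test that ignores it carries avoidable variance and its intervals are wider than they need be.

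This would matter most where the plan has least reserve. Stated Induction power covers only 200 mg against placebo at 0.05 (SAP 1.3). The key secondaries, and the co-primaries for 100 mg, are first tested at 0.025 (SAP 3.5) with no stated power.

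**Working it through.** **Inputs from the documents.** 220 per arm; CDAI remission 45% v 25%; PRO2 remission 30% v 15%; endoscopic response 25% v 10%; two-sided 0.05 for 200 mg and an initial 0.025 for 100 mg; overall power as the product of the two endpoint powers (SAP 1.3, 3.5).

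**Assumption.** The within-arm correlation ρ between baseline score and outcome, on a latent normal scale, is not in the documents. I use 0.2, 0.3 and 0.5.

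**Step 1: reproduce the stated power.** With d the difference, p̄ the mean rate and q = 1 − p,

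power = Φ{[d − z·√(2p̄q̄/n)] / √[(p₁q₁ + p₀q₀)/n]}.

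- CDAI: (0.20 − 1.96 × 0.0455)/0.0445 = 2.49, power 99.4%
- PRO2: (0.15 − 1.96 × 0.0398)/0.0392 = 1.84, power 96.7%
- Endoscopy: (0.15 − 1.96 × 0.0362)/0.0355 = 2.22, power 98.7%

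Non-EU joint: 0.9937 × 0.9869 = 98.1%, or 97.4% with a continuity correction (stated 97%). EU joint: 0.9669 × 0.9869 = 95.4%, or 94.0% with a continuity correction (stated 93%). The plan's figures reproduce to within about a point with the correction. The steps below use the uncorrected values.

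**Step 2: variance after adjustment.** If remission occurs when a latent score falls below an arm-specific threshold c, the remission probability at standardised baseline x is m(x) = Φ[(c − ρx)/√(1 − ρ²)]. The variance ratio is

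1 − [Var m₁(X) + Var m₀(X)] / (p₁q₁ + p₀q₀).

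| ρ | CDAI ratio | CDAI ratio, 15% non-responders regardless of baseline | PRO2 ratio |
|---|---|---|---|
| 0 | 1 | 1 | 1 |
| 0.2 | 0.976 | 0.98 | 0.979 |
| 0.3 | 0.946 | 0.96 | 0.952 |
| 0.5 | 0.847 | 0.88 | 0.861 |

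The third column scales m(x) by 0.85 and keeps the planned marginal rates. It mimics non-responder imputation that is unrelated to baseline; the 15% is assumed.

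A simulation of a logistic model standardised to a risk difference (1,500 trials per setting) gave 0.985, 0.942 and 0.830 for CDAI and 0.963, 0.960 and 0.875 for PRO2, with essentially the same mean difference as the unadjusted estimate.

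**Step 3: what that buys.** For CDAI the first ratio column is worth 220 × (1 − ratio) = 5, 12 or 34 subjects per arm. The unadjusted 95% half-width is 1.96 × 0.0445 = 8.7 percentage points. Multiplied by the square root of the ratio it becomes 8.6, 8.5 or 8.0.

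| Comparison | Unadjusted | ρ = 0.2 | 0.3 | 0.5 |
|---|---|---|---|---|
| CDAI, 45% v 25%, 0.05 | 99.4% | 99.5% | 99.6% | 99.8% |
| Joint CDAI and endoscopy, 0.05 | 98.1% | 98.2% | 98.3% | 98.5% |
| Joint PRO2 and endoscopy, 0.05 | 95.4% | 95.7% | 96.1% | 97.1% |
| CDAI, 38% v 25%, 0.025 | 75.8% | 76.9% | 78.3% | 83.0% |

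The last row is illustrative. The documents give no 100 mg effect, and its variance ratios (0.977, 0.947 and 0.849) come from the same formula. No gain is credited to the endoscopic test in any row.

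**Limit of the calculation.** The comparator in Steps 2 and 3 has no strata. Whatever the three planned factors already explain should be subtracted.

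**The case against.** The strongest reply is that nothing here is broken. CMH stratified by the randomisation factors is valid, the Protocol and SAP specify it consistently, and the SAP revision history shows that the risk difference was deliberately aligned with it. That stands. A reader might infer bias or an inflated error rate, but the documents support neither.

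A reader might also infer that Induction is underpowered for 200 mg. It is not: stated power is 97% and 93%, and the 200 mg rows above move by less than two points.

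The subgroup list is tempting as proof that the sponsor regards baseline CDAI as prognostic. It is not proof, since the same list holds sex, age, race and region, and the revision history gives consistency of results as the reason for extending it. Use in the imputation model shows only that the score is to hand.

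Nor does the fixed-cut-off argument reach endoscopic response, which is already relative to the subject's own baseline. No gain was calculated for an SES-CD term.

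Finally, the change is not free. CMH is the protocol-specified test, the End-of-Induction review uses p-values on CDAI remission (Protocol 8.10, SAP 6.5), and a baseline score can be missing (SAP Appendix 3 requires at least four evaluable diary days). These points shape the fix but do not remove the concern.

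**Conclusion.** The concern holds as a matter of efficiency for CDAI and PRO2 remission in the Induction Studies. Adjusting for the baseline score would cut the variance of the CDAI risk difference by about 2% to 15% for ρ from 0.2 to 0.5, by about 2% to 12% with 15% baseline-independent non-response, and by somewhat less still once the planned strata are counted. At ρ = 0 there is no gain. The effect on 200 mg at the planned rates is close to nil. The practical value is narrower intervals and some reserve for the 100 mg and key secondary tests at 0.025. The size rests on the assumed correlation, and the power gain at 0.025 also on the illustrative effect.

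**What to change.** Before the study blind is broken (SAP 2.2), amend SAP 6.2.4 and Protocol 8.5.1, or list the change in SAP 6.6, as follows.

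- Analyse Induction CDAI remission and PRO2 remission, whether co-primary or key secondary, with a logistic model containing treatment, the stratification factors and the endpoint's own continuous baseline score: CDAI for CDAI remission, both subscores for PRO2 remission. Standardise to a marginal risk difference with a robust standard error.
- State a simple rule for a missing baseline score.
- Keep stratified CMH as the sensitivity analysis, and as the fallback if the model does not converge.
- State which test gives the End-of-Induction p-values.
- Say in SAP 6.3.2 which endpoints use the model and which stay with CMH. An SES-CD term for endoscopic response is optional.

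A continuous term is preferable to more CMH strata. Cohort A already has 3 × 2 × 2 = 12 cells and Cohort B 8, SAP 6.2.4 allows small strata to be merged, and a two-level split of the baseline score recovers only about 60% to 65% of the variance gain.

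Cost: no new data, but a protocol-level change and a model-based estimator in place of CMH. The summary remains a difference in proportions. Its average over the Full Analysis Set can differ slightly from the Mantel-Haenszel-weighted value if effects vary across strata.

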##### Cohort A Induction Study:

- Number of prior exposures to biologic agent (0, 1, > 1) as listed in [Appendix 2](#)
- Concomitant use of oral, systemically absorbed corticosteroids at Day 1
- Concomitant use of immunomodulators at Day 1

##### Cohort B Induction Study:

- Number of prior exposures to biologic agent ( $\leq 1$ , > 1) as listed in [Appendix 2](#)
- Concomitant use of oral, systemically absorbed corticosteroids at Day 1
- Concomitant use of immunomodulators at Day 1

For the Maintenance Study, a stratified CMH test will be used to compare the treatment effect between a filgotinib dose group and placebo among the subjects from Induction Cohorts A and B combined being treated with the same dose of filgotinib. The CMH test will be stratified by the following factors:

- History of exposure to a biologic agent, (Yes or No)
- Concomitant use of oral, systemically absorbed corticosteroids at maintenance baseline
- Concomitant use of immunomodulators at maintenance baseline

Stratification factors based on the clinical database will be used for the analysis. The stratified CMH chi-square p-value for each of the above comparison will be provided. Strata with low numbers of subjects might be aggregated for the analysis. The 2-sided 95% CI of clinical remission rate by CDAI and endoscopic response rate based on normal approximation method with a continuity correction will be provided for each treatment group. In addition, stratified proportion difference along with its 95% 2-sided CI using stratum-adjusted Mantel-Haenszel (MH) approach {Koch 1989} for each comparison will be provided as follows:

The stratified point estimates for difference in proportion of subjects achieving an endpoint between each filgotinib (F) treatment group and the placebo (P) group will be calculated following formula (1).

$$\hat{p}_F - \hat{p}_P = \frac{\sum W_h d_h}{\sum W_h} \quad (1)$$

where  $d_h = \hat{p}_{Fh} - \hat{p}_{Ph}$  is the difference in the proportion of subjects who achieved the endpoint between the filgotinib group and the placebo group in stratum  $h$  ( $h = 1, 2, \dots, K$ ), and  $W_h = \frac{n_{Fh}n_{Ph}}{n_{Fh}+n_{Ph}}$  is the weight based on the harmonic mean of sample size per treatment group for each stratum where  $n_{Fh}$  and  $n_{Ph}$  are the sample sizes of the filgotinib group and the placebo group in stratum  $h$ , respectively.

The 95% stratum-adjusted MH CIs will be calculated following formula (2).

$$\hat{p}_F - \hat{p}_P \pm Z_{1-\alpha/2} \cdot SE(\hat{p}_F - \hat{p}_P) \quad (2)$$

Where  $SE(\hat{p}_F - \hat{p}_P) = \frac{\sqrt{\sum W_h^2 \left( \frac{\hat{p}_{Fh}^*(1-\hat{p}_{Fh}^*)}{n_{Fh}-1} + \frac{\hat{p}_{Ph}^*(1-\hat{p}_{Ph}^*)}{n_{Ph}-1} \right)}}{\sum W_h}$ ,  $\hat{p}_{Fh}^* = \frac{m_{Fh}+0.5}{n_{Fh}+1}$ ,  $\hat{p}_{Ph}^* = \frac{m_{Ph}+0.5}{n_{Ph}+1}$ , and  $m_{Fh}$  and  $m_{Ph}$  are the number of subjects who achieved the endpoint from the filgotinib group and the placebo group in stratum  $h$ , respectively.  $Z_{(1-\alpha/2)}$  is the 97.5% percentile of normal distribution with  $\alpha = 0.05$ .

If the computed lower confidence bound is less than  $-1$ , the lower bound is defined as  $-1$ . If the computed upper confidence bound is greater than  $1$ , then the upper bound is defined as  $1$ .

The significance level specified in Section 3.5 will be used to declare a statistically significant treatment effect for a filgotinib dose group.

Bar charts of the proportions of subjects achieving clinical remission by PRO2 (EU), CDAI (non-EU) and endoscopic response at Week 10 (for the Induction Studies) and Week 58 (for the Maintenance Study) will be provided by treatment group with corresponding p-values.

In addition, the proportion of subjects with percentage reduction of  $\geq 25\%$  from Induction baseline in total SES-CD score will be summarized for Week 10 (Induction Studies) and Week 58 (Maintenance Study), respectively. The number of available segments with SES-CD score at baseline and Week 10, and change from baseline at Week 10 for Induction Studies will be summarized. Similarly, the number of available segments with SES-CD score at Induction baseline and Week 58, and change from Induction baseline at Week 58 for Maintenance Study will be summarized. The score for each segment will be displayed in a data listing. If there is a missing segment score, the reason of missingness (if available) will be included.

